 - Pain of procedure: To assess pain of procedure, we will use the 11 point Numeric Pain Rating Scale (NPRS). We expect that the patients receiving 10 injections will have less pain associated with the procedure. The patients will rate their level of pain immediately following the completion of bladder injections by selecting a whole number from 0 to 10 that represents their level of pain (0 is no pain at all and 10 is the most severe pain) during the procedure. This scale has been validated, and correlates similarly to other pain scales [7].
- Secondary endpoints: Secondary endpoints to be assessed will be efficacy, OAB symptoms (nocturia, urgency, and frequency), post void residual volume (PVR) at 2 weeks and 12 week post-procedure, disease specific bother, health related quality of life (HRQoL), the patient's perceptions of change, and adverse events as detailed below:
 - Efficacy: The reduction in mean urge incontinence episodes which will be calculated by averaging the amount of urge urinary incontinence episodes over 3 days as recorded in a bladder diary. Success will be defined as a greater than 50% reduction in urge incontinence episodes after intradetrusor Botox® based on 3-day bladder diaries collected at baseline and 12 weeks post-injection. This outcome measure is consistent with results reported in previous trials involving Botox® for overactive bladder [6].
 - Disease specific bother and HRQoL: To assess OAB symptoms other than incontinence and impact on quality of life, we will administer the Overactive Bladder Questionnaire Short Form (OABq-SF) at baseline, at 2 weeks, and at 12 weeks post-procedure. This is an abbreviated version of the Overactive Bladder Questionnaire (OABq) developed to evaluate the bother and health related quality of life for patients with overactive bladder. The OAB-SF contains 6 items to assess symptom bother and 13 items to assess HRQOL. This questionnaire is commonly used, and has been validated for use in clinical practice [8].
 - PVR at 2 weeks and 12 weeks: To measure PVR at 2 weeks and 12 weeks, we will use a bladder scanner which measures volume based on ultrasound. The provider may also chose to measure PVR by straight catheterization at his or her discretion.
 - Patient's Global Impression of Change (PGIC) scale: In order to help determine the clinical significance of change, we will utilize the PGIC scale [16] administered at 2 weeks and 12 weeks post-injection.

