 - Each patient's mean number of urge urinary incontinence episodes will be calculated by averaging the number of urge urinary incontinence episodes collected over 3 days as recorded on a bladder diary. This will be calculated pre-intervention at baseline and at 12 weeks. As previously described, "treatment success" is defined achieving greater than 50% reduction in the number of urge urinary incontinence episodes at 12 weeks after treatment with Botox®. A "treatment failure" will be defined as achieving less than 50% reduction in the number of urge urinary incontinence episodes at 12 weeks after treatment with Botox®. A "treatment failure" will be defined as achieving less than 50% reduction in the number of urge urinary incontinence episodes at 12 weeks after treatment with Botox®. Our hypothesis is that there will be more significantly "treatment responders" in patients receiving 20 injections compared to 10 injections. To assess for clinical significance Chi square (X²) will be used.

- OABq-SF and PGIC collected from the group receiving 20 injections and the group receiving 10 injections. The mean will be calculated for each of the outcomes and for each of the groups. The result will be compared using paired t-test.
- We will compare the mean number of patients with urinary retention and UTIs in patients in both groups (those receiving 20 injections and those receiving 10 injections). To test for significance we will use the t-test.

Interventions and Interactions

- This study will use the FDA approved dose for refractory overactive bladder which is 100 units of onabotulinum toxin A (Botox®).
- Per surgeon preference, a flexible cystoscope or a rigid cystoscope will be used to inject the Botox® in the wall of the bladder.
- Injections will be in a grid-like fashion.
- We will use a 3 day bladder diary obtained from the International Urogynecological Association (IUGA) for baseline and 12 week follow up. (Appendix 1)
- Immediately after the treatment, patients will be asked to rate their pain using the Numeric Pain Scale. Please see appendix.
- Patients will be assessed for adverse events, symptom specific and global quality of life using the form in the appendix.
- All surveys will be handed to the patients by nursing. Patients will fill out the forms before seeing a physician.

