Appendix 5: OAB Short Form for Bother to be completed at baseline, 2 weeks and 12 weeks.

Protocol version: 1 Page 18 of 21

MRN: DOB: Date:		
Since beginning treatment at this clinic, how would you describe the change (if any) in ACTIVITY LIMITATIONS, SYMPTOMS, EMOTIONS and OVERALL QUALITY OF LIF to your condition? (tick ONE box).		elated
No change (or condition has got worse)	[]	1
Almost the same, hardly any change at all	[]	2
A little better, but no noticeable change	[]	3
Somewhat better, but the change has not made any real difference	[]	4
Moderately better, and a slight but noticeable change	[]	5
Better, and a definite improvement that has made a real and worthwhile difference	[]	6
A great deal better, and a considerable improvement that has made all the difference	[]	7

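### PGIC is there to help judge whether change is clinically significant, but its only named analysis is an arm mean, which does not show how many women reported a worthwhile change

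*Protocol*

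**What the plan says.** **Purpose.** Protocol, Objectives, secondary endpoints: "In order to help determine the clinical significance of change, we will utilize the PGIC scale". It is "administered at 2 weeks and 12 weeks post-injection". The Calendar of Events agrees and shows no baseline PGIC.

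**Form.** Appendix 6 is a seven-box, ordered scale. Level 4 reads "Somewhat better, but the change has not made any real difference", level 5 reads "Moderately better, and a slight but noticeable change", and level 6 reads "Better, and a definite improvement that has made a real and worthwhile difference". Level 7 is stronger still. Level 6 is therefore the first that calls the change worthwhile.

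**Analysis.** Protocol, Statistical Analysis, item 2, treats OABq-SF and PGIC together: "The mean will be calculated for each of the outcomes and for each of the groups", then "The result will be compared using paired t-test". It gives no PGIC cut-off, proportion or category table. The urge-incontinence diary endpoint in the same item does have a success definition, a reduction of more than 50% at 12 weeks.

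**SAP.** The single analysis paragraph does not name PGIC. It provides frequencies, percentages and chi-square or Fisher tests for categorical variables, and a t-test or Mann-Whitney test for continuous ones. It does not say which class PGIC belongs to.

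**The concern.** The labels are ordered, but nothing makes the steps between them equal. Averaging gives the step from level 1 to level 2 the same weight as the step from 5 to 6, where the wording first turns to worthwhile benefit. Two arms can then share a mean and differ in how many women crossed that line.

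The reason given for including PGIC is to help interpret change clinically, and a count of women at the worthwhile levels does that more directly than an average category number. The trial could report no PGIC difference between 10 and 20 injections while leaving unknown whether the shares of women with worthwhile change were similar.

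The test is a second, smaller problem. The two arms are different women, so a paired test does not fit the comparison. A paired comparison with baseline is not available for PGIC either, because there is no baseline score.

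**Working it through.** The documents give no figure for PGIC, so there is none to reproduce. The sample size supplies the group sizes used in step 4.

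**1. Group sizes (Protocol, Sample Size: effect size 1, SD 2, 16 per arm, 20 after 20% dropout).** Significance level, sidedness and power are not stated. I assume two-sided 0.05 and 80%, and read the effect size as 2 points over SD 2.

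- n = 2 × (1.960 + 0.842)² × (2/2)² = 15.7, so 16 per arm. The exact t calculation gives 16.7, so 17.
- 16 / 0.80 = 20.

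The stated 16 and 20 are reproduced, for pain and not for PGIC.

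**2. What a mean allows.** Let p be the share at level 6 or 7, with scores from 1 to 7 and mean m.

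- Largest p: everyone at 6 or at 1, so 6p + 1(1 − p) = m and p = (m − 1)/5, for m up to 6.
- Smallest p: 0 if m is 5 or less. Otherwise everyone is at 7 or at 5, so 7p + 5(1 − p) = m and p = (m − 5)/2.

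| Mean | Smallest share at 6–7 | Largest share at 6–7 |
|---|---|---|
| 4 | 0% | 3/5 = 60% |
| 5 | 0% | 4/5 = 80% |
| 5.5 | 0.5/2 = 25% | 4.5/5 = 90% |
| 6 | 1/2 = 50% | 5/5 = 100% |

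**3. Constructed examples with equal means.**

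- *Extreme, 20 per arm.* Ten women at 6 and ten at 2: (60 + 20)/20 = 4.0. Twenty women at 4: 4.0. The difference in means is 0, while the shares are 10/20 and 0/20. Fisher p = 2 × C(20,10)/C(40,10) = 2 × 184,756/847,660,528 = 0.00044.
- *Milder, 16 per arm.* Four at 4, eight at 5, four at 6: (16 + 40 + 24)/16 = 5.0. Two at 2, three at 3, one at 4, seven at 6, three at 7: (4 + 9 + 4 + 42 + 21)/16 = 5.0. The shares are 4/16 and 10/16, Fisher p = 0.07.
- *Mann-Whitney on the extreme example.* The ten women at 6 exceed all twenty at 4 (10 × 20 = 200 pairs) and the ten at 2 exceed none. U = 200 of 400, p = 1.0. The ordinal test sees no more here than the mean does.

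**4. Precision of the proportion.** Near 50%, the 95% half-width for a difference is about 1.96 × √(2 × 0.25/n).

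- n = 16: 0.346, about 35 points.
- n = 20: 0.310, about 31 points.

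Under assumed shares (not from the documents), two-sided 0.05, normal approximation for n:

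| Assumed shares | n per arm for 80% power | Fisher power at 16 per arm |
|---|---|---|
| 70% vs 50% | 93 | 12% |
| 80% vs 50% | 39 | 28% |

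**The case against.** **The SAP may already cover it.** PGIC is a tick-box form, and the SAP promises frequencies and percentages for categorical data. This stands in part: a reader might infer that the plan rules out category counts, and the SAP does not support that. But it does not class PGIC as categorical and sets no cut-off, so the arm mean remains the only analysis named for it.

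**PGIC is not alone.** A reader might infer that PGIC is the only outcome on whether change matters to the woman. The protocol does not support that. OABq-SF measures bother and quality of life, the diary endpoint has a success threshold whose test is described in terms of clinical significance, and PGIC is given a helping role. Nor is a mean empty of clinical meaning, since one near 4 or 6 can be read against the labels.

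**The extreme example is contrived.** This stands. It sets a split arm against an arm with no spread. The milder pair gives p = 0.07. The examples show that a difference can be hidden, not that it is likely to be.

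**An ordinal test might seem enough.** A reader might infer that replacing the t-test with Mann-Whitney settles the matter. Step 3 shows that it does not. It suits independent arms and an ordered scale, but it does not by itself reveal the share with worthwhile change.

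**The cut at 6 and the emphasis on week 12 are review choices.** This stands. Level 5 could also be argued for, and the documents fix neither the cut nor a lead visit for PGIC.

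**The proportion is imprecise.** This stands too. It limits the proportion to description, but is no reason to leave it unreported.

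**Conclusion.** The concern holds as a minor one. The only analysis named for PGIC does not give the information most relevant to its stated purpose: a mean of 4 fits any share from 0% to 60% at levels 6 and 7, and a mean of 5 any share from 0% to 80%. These bounds depend only on the 1-to-7 scoring and on taking 6 as the first worthwhile level, which is how Appendix 6 words it.

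The documents do not support a claim that the trial will miss a real difference in benefit, or that the PGIC mean is meaningless. PGIC is an unpowered secondary endpoint, and the primary pain conclusion is unaffected.

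**What to change.** In Protocol, Statistical Analysis, item 2, and in the SAP, separate PGIC from OABq-SF and specify:

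- for each arm, the number and percentage in each of the seven categories;
- for each arm at week 12, the number and percentage scoring 6 or 7, with the between-arm difference and an exact 95% CI, read as descriptive; week 2 reported the same way as supportive;
- an unpaired Mann-Whitney test on the seven-level score in place of the paired t-test, with PGIC named, because the SAP lists that test only for continuous variables.

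**Cost.** A few lines in both documents and one table. No new data or visits are needed, since individual scores are already collected at weeks 2 and 12.

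**Downsides.** Cutting at 6 discards information, so the full distribution and ordinal test stay beside it. The cut rests on the form's wording and should be described so. The interval will be wide, about 31 to 35 points either side at 20 to 16 per arm. The SAP is written in the past tense, which suggests that the analysis may already have been done; if the cut is set after data were seen, it must be labelled post hoc.

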Adverse events: Specific to intradetrusor injections of Botox®, the most common adverse events are urinary retention requiring intermittent catheterization (approximately 4%) [9] and urinary tract infections (approximately 15.5%-35%) [10]. Patients will be closely monitored for urinary tract infections as they will undergo urinanalysis and assessment of symptoms at their post-operative visits.

Methods and Measures

- Design:
 - This study is a randomized clinical trial to assess whether or not 10 injections of 100 units of intradetrusor Botox® toxin is perceived as less painful compared to 20 injections of 100 units of intradetrusor Botox® toxin for the treatment of refractory OAB. Refractory OAB is defined as persistent urinary frequency and urgency despite behavioral modifications, failing a trial of 2 medications (anticholinergics or beta 3 agonists), have a contraindication to the medications, or are unable to tolerate medications due to allergies or side effects.
 - The primary outcome will be assessed by the patient completing the pain of procedure questionnaire, the NPRS, to be completed by the patient immediately after the procedure. The patient will receive the questionnaire from the nurse or medical assistant after the provider has performed the procedure. We will then compare mean value of the NPRS for the 10 injection group to the 20 injection group.
 - Efficacy will be assessed by comparing study participant's reduction in urge urinary incontinence episodes based on a 3 day voiding diary to be shared by the participant at baseline and 12 weeks post-procedure. This diary is dispensed to all patients during their visit prior to procedure visit as a part of standard of care. If subjects demonstrate a 50% reduction in urge incontinence episodes on a 3-day bladder diary, they will be categorized as "treatment success" whereas those who do not will be categorized as "treatment failure." This dichotomous outcome will define efficacy as a secondary endpoint.

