 - All eligible participants will be considered for the study. Patients will be counseled about the study in the office setting. Upon enrollment, patients will share a 3-day voiding diary. Diary is dispensed to all patients when they decide to undergo injection procedure. Disease specific bother and health related quality of life questionnaires will be completed following consenting. As per standard of care, urinalysis and post-void residual volume will be measurement. The only assessment in this list that is not part of standard clinical care are the questionnaires. If patients are on medications for

overactive bladder, they will be required to stop at least 3 weeks prior to undergoing the baseline 3 day voiding diary.

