After consenting to enrollment in the study, the patients will be scheduled for Botox® injections in the office. Randomization will be performed using random sequence number generation in blocks of 10 with randomization assignment concealed in sequentially numbered opaque envelopes. Randomization will be performed before the study startup by the coordinator using online available tool (sealed envelope). Envelopes with 50% carrying 10 injections instructions, and 50% carrying 20 injections instructions are prepared in advance, sealed, numbered 1 to 50, and stored in a locked cabinet at the Urology clinic at [name]. Three envelopes will be carried to the Greensboro Wake Health System during coordinator's scheduled clinic days. And then coordinator will bring those packets back to the [name] Urology clinic on a regular base. On the day of the procedure, the provider will select the next numbered envelope that will contain the randomization assignment for the number of injections. Subjects will be blinded to the randomization result. All patients will undergo a urinalysis prior to the procedure. If there is concern for an acute, untreated urinary tract infection, the patient does not undergo the procedure, and is treated with antibiotics while a urine culture is sent. All participants will be given preoperative antibiotics (except aminoglycosides). 100 units of Botox® will be combined with 20 cc saline for the purposes of 20 injections, or 100 units of Botox® will be combined with 10 cc of sterile saline for the purpose of 10 injections. Lidocaine Jelly locally. And the bladder will be instilled with 30ml of Marcaine and 5ml of NaHCo3 solution through a catheter for at least 15 minutes prior to the procedure. Cystoscopy with either a rigid or flexible cystoscope (per surgeon preference) will be performed using sterile technique. The Botox® will be injected in a grid like pattern avoiding the trigone as seen below. Study patients do not know the number of injections received in the bladder. There are two providers in the room for each procedure. Injection counting will be verbalized as Injection 1, Injection 2... to up to Injection 20 by non-injecting provider. A patient and a provider who is injecting will hear total of 20 counts. Providers will know the randomization prior to procedure, and a decision will be cleared between two providers whether to account pseudo injection at odd or even number for patients receiving 10 injections. A patient randomized to 10 injections will receive 10 injections at alternate count. All patients will be informed in advance about the procedure at the time of consenting. The patient will be allowed to void on her own postprocedure. Immediately after the procedure, the patient will receive a questionnaire to rate the pain of procedure using the numeric pain scale. The patient will then be discharged to home. Figure 1: Diagram showing sites of injections for patients undergoing 10 injections of 100 units of Botox®.

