
Figure 1: Diagram showing sites of injections for patients undergoing 10 injections of 100 units of Botox®.

[figure not shown]

Figure 2: Diagram showing sites of injections for patients undergoing 20 injections of 100 units of Botox®

- At two weeks, the patient will return to clinic for a standard office visit. She will have a post void residual checked using either a bladder scan or catheter, and a urinalysis (urine culture will be sent per clinic protocol). If a urine culture grows any bacteria, and the patient is symptomatic, she will be treated with culture specific antibiotics. She will then be asked about symptoms of a urinary tract infection, if they have been treated for a urinary tract infection, difficulty emptying the bladder, or required intermittent or an

indwelling Foley catheter since the Botox® therapy. Subjects will complete the PGI-C and the OAB-SF. The patient will be sent home with a 3-day bladder diary to complete just prior to the 12-week visit.

- At 12 weeks, the patient will return to clinic and her 3-day bladder diary will be reviewed. A post void residual volume will be checked using either a bladder scan or catheter, and a urinalysis will be sent per standard practice (urine culture will be sent per clinic protocol). If a urine culture grows any amount of bacteria and the patient is symptomatic, she will be treated with culture specific antibiotics. She will then be asked about symptoms of a urinary tract infection, if they have been treated for a urinary tract infection, difficulty emptying her bladder, or required intermittent or an indwelling Foley catheter since the Botox® therapy. She will again take the OABq-SF and PGIC.
- Setting:
 - This study will take place at two Urology clinic locations at Wake Forest Baptist Medical Center, [name] in Winston Salem, NC and [name] in Greensboro, NC.

Subjects Selection Criteria

- Inclusion criteria: Subjects must meet the following inclusion criteria in order to be eligible for the study
 - 1. Female gender
 - 2. At least 18 years of age
 - 3. Have already decided to undergo intradetrusor Botox® injections for treatment of refractory overactive bladder.
 - 4. Able and willing to learn clean intermittent catheterization (or care provider is willing and able to perform intermittent catheterization).
 - 5. Understands and is willing to undergo follow up and complete questionnaires as described in this protocol
 - 6. Able to give informed consent

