Confidentiality and Privacy: Confidentiality will be protected by collecting only the information needed to assess study outcomes, minimizing the collection of any information to the fullest extent possible that could directly identify subjects, and maintaining all study information in a secure manner. To help ensure subject privacy and confidentiality, only a unique study identifier will appear on the data collection form. Any collected patient identifying information corresponding to the unique study identifier will be maintained on a linkage file, stored separately from the data. The linkage file will be kept secure, with access limited to designated study personnel. Following data collection, subject identifying information will be destroyed 3 years after closure of the study by shredding, consistent with data validation and study design, producing an anonymous analytical data set. Data access will be limited to study staff. Data and records will be kept locked and secured, with any computer data password protected. No reference to any individual participant will appear in reports, presentations, or publications that may arise from the study.

Data and Safety Monitoring: The principal investigator will be responsible for the overall monitoring of the data and safety of study participants. The principal investigator will be assisted by other members of the study staff.

Reporting of Unanticipated Problems, Adverse Events or Deviations: Any unanticipated issues, serious and unexpected adverse events, deviations or protocol changes will be promptly reported to the principal investigator or member of the research team, the IRB, sponsor, and appropriate government agency if appropriate.

Bladder Diary Sample

This simple chart allows you to record the fluid you drink and the urine you pass over 3 days (not necessarily consecutive) in the week prior to your clinic appointment. This can provide valuable information.

Please fill in approximately when and how much fluid you drink and the type of liquid.

Please fill in the time and amount (in mls, or ounces) of urine passed, and mark with a star if you have leaked or mark with a "P" if you have needed to change your pad.

Here is an example of a filled chart to help you complete your own more easily.

Date/Time DD.MM.YY	Liquid Intake (ml)	Volume of Urine (ml)	Leaks	Pad Change
21.02.06			*	
0215		150		
0715		250		
0800	1 cup of coffee		þ.	
0820		60	*	Р
0930	Cup orange juice		*	
1000		100		

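### Efficacy is defined on urge incontinence episodes, but the named diary records only that a leak occurred, and no step shown separates urge leaks from other leaks

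*Protocol*

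**What the plan says.** **Endpoint.** Protocol, Objectives (Efficacy), defines the outcome as mean urge incontinence episodes, "calculated by averaging the amount of urge urinary incontinence episodes over 3 days as recorded in a bladder diary", with success at more than a 50% reduction from baseline to week 12. Protocol, Statistical Analysis, repeats the source of the count: "averaging the number of urge urinary incontinence episodes collected over 3 days as recorded on a bladder diary".

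**Instrument.** Protocol, Interventions and Interactions, names it: "We will use a 3 day bladder diary obtained from the International Urogynecological Association (IUGA) for baseline and 12 week follow up". It refers to Appendix 1, where the Bladder Diary Sample tells the patient: "Please fill in the time and amount (in mls, or ounces) of urine passed, and mark with a star if you have leaked". A separate letter marks a pad change. The columns are date and time, intake, urine volume, leaks and pad change. The blank patient form is only partly reproduced in the text available, but its readable header has the same columns.

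**Handling.** On the baseline diary, the Design section says: "This diary is dispensed to all patients during their visit prior to procedure visit as a part of standard of care". Subject Recruitment Methods adds that it is reviewed to extract its information, and the Calendar of Events has the completed diary collected on the procedure day. At week 12, "the patient will return to clinic and her 3-day bladder diary will be reviewed". None of these places mentions leak type. The SAP lists tests and does not mention the diary.

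**The concern.** The endpoint needs a distinction that the instrument does not record. A leak on coughing and a leak with sudden urgency receive the same star. Both can occur in this population. None of the 12 exclusion criteria concerns stress or mixed incontinence, and the Design section defines refractory overactive bladder by frequency and urgency, not by type of leakage. The trial's own OAB-q SF treats the distinction as meaningful, because it asks about accidental small losses (bother item 3) separately from loss with a strong desire to void (bother item 6).

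If leak type was not captured at review, the responder rate describes all leaks while being reported as urge-specific. Women with mixed leakage can then be misclassified in either direction. A star on a completed diary cannot be sorted by type afterwards from the diary alone.

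**Working it through.** **1. The plan's own figure.** No sample size or power is given for efficacy. The only stated figure is for pain: 16 per group, 20 after 20% dropout. The inputs are an effect size of 1 (2 points over an SD of 2). Two-sided 5% and 80% power are my assumptions, since neither is stated.

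- n = 2 × (1.960 + 0.842)² / 1² = 15.7, so 16 per group.
- 16 / 0.8 = 20.

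The figure reproduces and does not depend on this point. It is used below only for the numbers per arm.

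**2. Can any form shown supply an urge count?**

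| Source | What it records | Urge episodes countable? |
|---|---|---|
| Appendix 1 diary | A star for any leak | No |
| Diary review, baseline and week 12 | No rule for leak type | Not documented |
| OAB-q SF bother item 6 | Graded bother over 4 weeks | No |
| Adverse event form, PGIC, SAP | Nothing on leak type | No |

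**3. Effect on one patient (hypothetical counts; the documents give no share of non-urge leaks).** Take 18 leaks at baseline and 10 at week 12. The all-leak fall is 8/18 = 44%, a failure. If k leaks at each visit are non-urge and unchanged, the urge fall is 8/(18 − k):

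| k | Urge fall | Class |
|---|---|---|
| 0 | 44% | failure |
| 1 | 8/17 = 47% | failure |
| 2 | 8/16 = 50% | depends on the section read |
| 3 | 8/15 = 53% | success |
| 5 | 8/13 = 62% | success |

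The case k = 2 is unclear because the Objectives require more than 50%, the Design section accepts a 50% reduction, and the Statistical Analysis leaves exactly 50% in neither class. The argument does not need that row.

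The error can also run the other way. A fall from 18 to 8 is 10/18 = 56%, an all-leak success. If non-urge leaks happened to go from 4 to 0, urge leaks went from 14 to 8, a fall of 6/14 = 43%, a failure.

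**4. General form.** If a share s of baseline leaks is non-urge and unchanged, all-leak fall = (1 − s) × urge fall. To pass a 50% threshold on all leaks, the urge fall must exceed 0.5/(1 − s):

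| s | Urge fall needed |
|---|---|
| 0 | 50% |
| 0.1 | 55.6% |
| 0.2 | 62.5% |
| 0.3 | 71.4% |

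A true urge fall of 60% reads as 54% at s = 0.1 (success) and 48% at s = 0.2 (failure). With s = 0 there is no effect.

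**5. Size against sampling error.** One misclassified woman is 1/20 = 5 points of her arm's success rate, or 1/16 = 6.25 points. The largest standard error of a difference in success rates is √(2 × 0.25/n): 15.8 points at n = 20 and 17.7 at n = 16. A few misclassified women would not be visible in the result.

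**6. Why leaving unmarked leaks uncounted is not enough.** Suppose all leaks are urge leaks. A true fall from 18 to 10 (44%, failure) with two marks forgotten at week 12 becomes 18 to 8 (56%, false success). A true fall from 18 to 8 (56%, success) with three marks forgotten at baseline becomes 15 to 8, 7/15 = 47% (false failure).

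**The case against.** The strongest reply is that the step may exist and simply not be written down. Review is planned at both time points, and staff could ask about each star. The Study Inclusion Form, the Completion of Study Form and the data collection form are named but not reproduced. This stands, and it limits the point: classification is undocumented in what is shown. A reader might infer that all leaks were in fact counted and reported as urge episodes. The documents do not establish that.

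A reader might also infer that the efficacy comparison is biased towards one arm. That is not supported either. Patients are blinded and use the same form in both arms, and nothing shown makes their recording differ by arm. It is true that "Providers will know the randomization prior to procedure", but no section says that providers classify leaks. The share of non-urge leaks is unknown, and misclassification can go either way.

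OAB-q SF item 6 gives an urge-specific bother rating at baseline, 2 and 12 weeks. It is a useful cross-check but not an episode count. Finally, the SAP is dated 7/31/23 and written in the past tense, so a change to the form may come too late. That too stands, and leaves the request for clarification as the part most likely to be usable.

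**Conclusion.** The point holds as a limited one. The endpoint is urge-specific, the named diary is not, and no rule shown connects them, so following the plan literally gives an all-leak count under an urge label. For an individual the classification can change with a small number of non-urge leaks (3 of 18 in the hypothetical case). For the trial, the size and direction of any effect on the arm difference cannot be determined.

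This rests on two assumptions: that some enrolled women have non-urge leaks, which the criteria allow but the documents do not quantify, and that the unreproduced parts of the forms hold no leak-type field. It concerns one secondary endpoint in a trial sized for pain. The primary endpoint and the sample size are untouched. It is worth considering, with medium confidence.

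**What to change.** **For diaries still to be completed.**

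- On the study diary at baseline and week 12, have each leak marked 'U' (with urge) or 'N' (not with urge).
- Resolve unmarked leaks with the patient at the review already planned. Use existing staff unaware of the allocation where possible. That rules out the providers, and also the coordinator if she or he knows the sequence, since the coordinator prepares the randomization and carries the envelopes.
- State that U leaks define efficacy.
- Fix one rule for leaks still unclassified, for example counting them as urge, and apply it identically at both visits and in both arms. Report their number by arm and visit.
- Give the all-leak count as a sensitivity analysis.

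**For diaries already collected.** State in one sentence how urge episodes were identified. If leak type was not captured, report the endpoint as all incontinence episodes.

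**Cost.** One extra mark per leak, a short question at an existing contact, and a small change to a standard-of-care form or a study copy of it. Leak type recalled at review is less reliable than a mark made at the time. Where the endpoint is renamed, the urge-specific measure is lost. No repeat baseline diary is requested: patients on overactive bladder medication have a condition tied to that diary ("they will be required to stop at least 3 weeks prior to undergoing the baseline 3 day voiding diary"), and a repeat could lengthen that period or delay the procedure.
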